Clinical Investigational Plan

Zimmer Knee Creations SCP® Observational Cohort Follow-Up Study

Version 2: August 24, 2016

Sponsor:
Zimmer Knee Creations
[name]
[name]

1. Protocol Synopsis

| | |
|------------------------------|---|
| Study Title | Zimmer Knee Creations SCP® Observational Cohort Follow-Up Study |
| Study Nickname | SCP® Observational Study |
| Study Design | Multi-center patient outcome observational cohort |
| Sponsor | Zimmer Knee Creations |
| Protocol Number | KC.CR.I.AM.16.3 |
| Protocol Version | 2 |
| Number of Sites | Approximately 30 |
| Number of Patients | Approximately 1000 |
| Inclusion Criteria | 
1. Surgeon considers patient appropriate for SCP® procedure.2. Patient has agreed to undergo the SCP® procedure or has already undergone the procedure.3. Subject is willing and able to sign a written consent form.4. The subject has the mental capacity and the willingness to contribute follow-up outcome data.5. Patient is willing and able to complete outcome forms in person or by phone, email or regular mail. |
| Evaluation Parameters | 
1. Detailed Patient Demographic Information2. Work/disability status3. Operative details4. Safety (i.e. adverse events)5. Visual Analog Scale (VAS)—Knee Pain6. International Knee Documentation Committee (IKDC) Subjective Knee Form7. VR-12 Health Survey8. Secondary Surgical Intervention |

2. Description of SCP® Procedure

Subchondroplasty® (SCP®) is a procedure performed on subjects who have bone marrow lesion(s) (BML). BMLs are subchondral defects in the bone and the SCP procedure allows surgeons to place AccuFill® calcium phosphate (CaP) (bone void filler) at the defect site. SCP is performed on the subchondral bone of the knee utilizing an arthroscopic/percutaneous approach. Using standard arthroscopic surgery techniques, skin incisions are made for the insertion of arthroscopic instrumentation. Other arthroscopic procedures in the knee are performed per the surgeon's operative plan for each subject. Using fluoroscopic guidance, the surgeon locates the BML and one or more AccuPort cannulas are drilled into the bone. Through the cannula, calcium phosphate bone void filler is injected into the bone marrow lesion until the edematous region is

filled. The calcium phosphate fills the edematous void (defect) and hardens within the BML. The calcium phosphate is resorbed over time and replaced with natural bone.

3. Study Design

This is a multi-center patient outcome observational cohort study intended to collect data on the short- and long-term safety and effectiveness of the SCP procedure. This observational cohort will become a repository of data reflecting patient experiences with the SCP procedure over time. Detailed patient demographic information (e.g., age, gender, location of defect, severity of symptoms, etc.) will be collected to determine the most suitable SCP patient population(s). The study duration is expected to be 10 years.

3.1 Study Population

The SCP Observational Cohort study will enroll either patients undergoing SCP or patients who have already had the SCP procedure for the treatment of BMLs where bone void filler is placed at the site of the BML (defect).

3.2 Study Sites

The study will be conducted at up to 30 sites. All will be trained on the SCP Observational Cohort study.

3.3 Sample Size

As an observational cohort study there is no upper subject enrollment limit. Every patient undergoing the SCP procedure will be invited to participate in the study. The study goal is to collect data for approximately 1000 patients and evaluate demographics and outcomes data.

4. Study Procedures

4.1 Subject Eligibility

Enrollment will be based on the treating physician's standard of care and the following criteria:

1. Surgeon considers patient appropriate for SCP procedure.
2. Patient has agreed to undergo the SCP procedure or has already undergone the procedure.
3. Subject is willing and able to sign a written consent form.
4. The subject has the mental capacity and the willingness to contribute follow-up outcome data.
5. Patient is willing and able to complete outcome forms in person or by phone, email or regular mail.

4.2 Subject Enrollment

All patients considered for the SCP procedure by the investigator or who have had the SCP procedure will be invited to participate in the study. Patients expressing an interest in participation will proceed with the informed consent process. No study activities will be performed prior to patient signature of the informed consent form. If the patient does not sign the informed consent, the patient will still undergo the SCP procedure, but they will not be included in the observational cohort study. Should a patient not undergo SCP, the patient will not be enrolled in the observational cohort study and will be reported as a screen fail. The enrollment status for each patient considered in the study will be appropriately documented on a screening log.

4.3 Subject Informed Consent

Patients will provide written consent to be included in the SCP study. The informed consent form will conform to 21 CFR Part 50, Protection of Human Subjects. Each patient must read, have an opportunity to have any questions addressed, and sign this form prior to being enrolled in the study.

The investigator or appropriate study staff's signature on the consent form will document that the informed consent process included the following items:

- The subject was provided adequate time to read and review the consent form prior to signing it.
- The subject was given an opportunity to ask any questions he/she had concerning the study.
- The subject understands what their expectations are for participating in the study.
- The information in the consent form was provided in a language the subject understands.
- The subject signed the consent form prior to enrollment in the observational cohort study.
- The subject received/will receive a copy of the signed and dated consent form.

4.4 Data Collection

This section is applicable to individuals who have undergone screening, have signed an Informed Consent Document, and have otherwise been found eligible to participate in this study. This section details the pre-operative, operative, and post-operative management of Subjects.

In order to minimize the burden to patient and physician, patients will be enrolled at the physician's office, but will not be required to come back to the office for follow-up visits. The follow-up data to be collected as part of this study will be mailed or emailed to study

subjects by their study doctor at the selected time points (6 weeks, 3 months, 6 months, 1 year, 2 years, 3 years, 4 years, and 5 years). The patient will fill out the evaluation forms and then mail the forms back to their study doctor or complete them online. These forms may also be completed by phone with study staff; however an approved phone script must be used. Additionally, if the subject returns to the physician's office during a follow-up time point, the evaluation forms may be completed in person.

Zimmer Knee Creations will work with an electronic data capture (EDC) system developed to track all patient data for this observational cohort study. The EDC firm will complete the necessary diligence to ensure any platform selected meets the technical, reporting, data management, storage and security needs of the firm. Data collected on the CRFs will be included in the study database.

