4.4.3 Postoperative Procedures

Immediate post-operative management is at the discretion of the surgeon and support staff and should follow each Site's standard of care.

Data collection for this study will occur post-operatively at 6 weeks, 3 months, 6 months, 1 year, 2 years, 3 years, 4 years and 5 years. The post-operative visit data listed in Table 3 must be collected for each enrolled Subject either in person or by email, mail or telephone.

Table 3: Postoperative Data Collection

| Form 4—Post-Operative Evaluation | |
|---|---|
| Evaluation | Details of Evaluation |
| VAS—Knee Pain | |
| Medications | |
| Surgical/Non-Surgical Procedures | Each of the questionnaires should be completed by the Subject. It typically takes 5-10 minutes per questionnaire to complete. |
| Work/Disability Status | |
| IKDC | |
| VR-12 Health Survey | |
| Adverse Event (if applicable) | 
Only AEs which are possibly or definitely related to the device or procedure will be reported to the sponsor.
 
Serious AEs must be reported as soon as possible and within 24 hours after the investigator first learns of the event. The Sponsor is subsequently responsible for reporting as required.
 
See Adverse Event Reporting in Section 5.
 |
| End of Study/Withdrawal | At any time during the study a Subject may withdraw. Subject withdrawal must be documented and provided to the Sponsor. |

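### Does allowing the follow-up knee-pain VAS to be completed by phone, with no stated mode field or mode analysis, call for a change to the plan?

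*Combined protocol and SAP*

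**What the plan says.** The synopsis lists knee-pain VAS among eight evaluation parameters, and Table 3 (section 4.4.3) places it on Form 4. It is due at eight follow-up points: "6 weeks, 3 months, 6 months, 1 year, 2 years, 3 years, 4 years and 5 years". The enrolment target is in section 3.3: "The study goal is to collect data for approximately 1000 patients and evaluate demographics and outcomes data".

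Section 4.4 sets the default route. Forms go out to patients by post or email, and then: "The patient will fill out the evaluation forms and then mail the forms back to their study doctor or complete them online". Phone is the added route: "These forms may also be completed by phone with study staff; however an approved phone script must be used". In-person completion is allowed when a patient happens to be at the office. Section 4.4.3 confirms the range of routes for the Table 3 data, which "must be collected for each enrolled Subject either in person or by email, mail or telephone". Tables 1 and 3 both say that the patient is the one who completes the questionnaires.

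On data capture, section 4.4 says only: "Data collected on the CRFs will be included in the study database". The form tables list no completion-mode item. Section 4.4.1 names no mode for the baseline questionnaires on Form 2. Section 4.5 is a single sentence that foresees covariate analyses on factors such as age, sex, defect site and symptom severity; mode is not among those named.

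**The concern.** A VAS is normally a mark placed on a line that the patient can see. On a call, a patient without the form in view has to give a spoken number, and a staff member hears the answer. Either could move the rating. If phone use differs between time points, or between the subgroups compared under section 4.5, part of an apparent VAS difference could come from how the rating was obtained. A bias of that kind does not shrink as enrolment grows.

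There is also a point about timing. Mode that is not captured when the form is completed can later be only partly rebuilt, from returned paper, online records and contact logs. With about 1000 patients and eight time points, up to 8,000 scheduled ratings carry no stated requirement to record it.

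**Working it through.** **What the protocol supplies.** Patients: about 1000 (section 3.3). Follow-up points: 8 (section 4.4.3). Scheduled ratings: 1000 × 8 = 8,000. This is a ceiling. Sections 3.1 and 4.1 admit patients who have already had the procedure and may be past the early time points, and section 7.1 allows participation to end at revision, withdrawal or death.

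**What it does not supply.** Scale length, SD, phone share and phone offset are all absent. The 1000 is a collection goal with no power or precision inputs, so there is no stated figure to reproduce. Everything below is illustration under assumptions.

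**Assumptions.** 0-10 scale; baseline entirely self-completed; SD of change 2.5 to 3.0; phone offset 0.5 to 1.0 point, sign unknown; phone share 10% to 30% (800 to 2,400 of the 8,000 ratings).

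**Shift in mean change** = phone share × offset.
- 10% phone: 0.10 × (0.5 to 1.0) = 0.05 to 0.10.
- 30% phone: 0.30 × (0.5 to 1.0) = 0.15 to 0.30.

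If some baselines were also taken by phone, the relevant share is follow-up share minus baseline share, and the shift is smaller.

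**95% half-width of a mean change** = 1.96 × SD / √n.

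| n | SD 2.5 | SD 3.0 |
|---|---|---|
| 1000 | 0.155 | 0.186 |
| 600 | 0.200 | 0.240 |

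At 10% phone the shift is below all four values. At 30% phone with a 0.5 offset it is 0.15, still just below the smallest. At 30% phone with a 1.0 offset it is 0.30, above all four. At 30% phone the shift equals the half-width when the offset is 0.155 / 0.30 = 0.52 (n = 1000, SD 2.5) and 0.240 / 0.30 = 0.80 (n = 600, SD 3.0).

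**Subgroup contrast**, the use closest to section 4.5. Take 500 v 500 with 10% v 30% phone. Shift = (0.30 − 0.10) × (0.5 to 1.0) = 0.10 to 0.20. Half-width = 1.96 × 2.5 × √(2/500) = 0.31. The shift stays below it.

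**A different set of assumptions.** On a 0-100 scale with phone share 10% to 40% and offset 2 to 10 points, the pooled mean moves by 0.2 to 4.0 points. With SD 20 to 30 the half-width is 1.24 to 1.86 at n = 1000 and 1.60 to 2.40 at n = 600. The picture is the same: negligible at low phone use, larger than sampling error only when both share and offset are high.

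**What a mode comparison could show.** Half-width of the phone v non-phone difference at one time point, SD 2.5:
- n = 1000, 10% phone: 1.96 × 2.5 × √(1/100 + 1/900) = 0.52.
- n = 1000, 30% phone: 1.96 × 2.5 × √(1/300 + 1/700) = 0.34.
- n = 600, 10% phone: 1.96 × 2.5 × √(1/60 + 1/540) = 0.67.
- n = 600, 30% phone: 1.96 × 2.5 × √(1/180 + 1/420) = 0.44.

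At 10% phone, a 0.5-point offset lies inside the margin of error at either sample size.

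**The case for a change.** The strongest case for a change is that recording mode is cheap and that what is not recorded may not be fully recoverable. The study's stated purpose includes effectiveness and finding suitable patients, so ratings should be comparable across patients and over time. Phone use is unlikely to be random: sections 6 and 7.2 list phone calls among the contact attempts for patients who have not returned forms, so phone ratings may cluster in patients who are harder to reach. Section 8 does not collect minor deviations, so a small departure from the script would leave no entry in the violation log. And a script standardises the wording of a call without, by itself, putting mode into the database.

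Much of this stands as description. The protocol is silent on all three points, and a mode field would be a sensible thing to find on Form 4. It does not show that a stated rule gives a wrong result. The script is mandatory and is the natural place for the spoken VAS rating; the CRFs and data capture system are the natural place for mode. Their contents are unknown, so a gap in them is not established. Because section 4.4 has forms sent out at each time point ("The follow-up data to be collected as part of this study will be mailed or emailed to study" subjects), a phone respondent may well have the scale in hand. Paper returns and online entries leave their own trace, which limits what would be lost.

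The point about non-random phone use also works against the proposed analysis. If phone respondents differ in responsiveness, leaving them out changes the patients as well as the mode, and the resulting difference cannot be read as a mode effect.

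**Conclusion.** No change to the plan follows. The protocol allows phone completion of the VAS under a required script and leaves the rating method and any mode field to operational documents that are not shown. That is missing detail which sites, data managers and analysts ordinarily fill. The absence of a mode analysis is one instance of a broader brevity: section 4.5 defines no primary endpoint, VAS summary or model for any outcome, so there is no specified VAS analysis for a mode check to accompany.

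Offering several routes is a deliberate trade-off. Section 4.4 gives minimising burden on patient and physician as the reason for not requiring office follow-up visits, and a phone rating is worth more than a missing one in a follow-up of five years.

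The gain from a change would be small. The main summary would keep every patient and would not be adjusted for mode, so the headline result would be the same. The extra sensitivity result would not isolate a mode effect, and at 10% phone use its precision (±0.52 at n = 1000) would not resolve a 0.5-point offset. On the 0-10 illustration the shift is 0.05 to 0.10 at 10% phone and 0.15 to 0.30 at 30%, against half-widths of 0.155 to 0.240; it exceeds them only when phone use and offset are both towards the upper end. All SDs, shares and offsets are assumptions. The true size and direction cannot be derived from the document, and the half-width is only a yardstick, since bias does not fall with n.

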4.4.1 Preoperative Procedures

Prior to surgery, the data in Table 1 must be collected for each enrolled Subject.

Table 1: Preoperative Data Collection

| Form 1—Medical History | |
|--------------------------------|---|
| Evaluation | Details of Evaluation |
| Enrollment Checklist | Authorized medical personnel will verify subject eligibility. |
| Patient Demographics | Authorized medical personnel will collect basic demographics from the preoperative time period. |
| Knee Related History | Authorized medical personnel will collect previous/current treatments and previous/current medications (prescription drugs) for the affected knee, as well as previous surgical treatments. |
| Concomitant Medical Conditions | Authorized medical personnel will collect medical conditions from the preoperative time period. |
| Current Medications | Authorized medical personnel will collect current medications (prescription drugs) not related to the affected knee. |

| Form 2—Pre-Operative Clinical Evaluation | |
|---|---|
| Evaluation | Details of Evaluation |
| VAS—Knee Pain | Each of the questionnaires should be completed by the Subject. It typically takes 5-10 minutes per questionnaire to complete. |
| Length of Painful Symptoms | |
| Work/Disability Status | |
| IKDC | |
| VR-12 Health Survey | |

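### Section 4.4.1 demands a pre-surgery baseline from every enrolled subject, but already-operated patients are eligible and the protocol names no baseline source for them

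*Combined protocol and SAP*

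**What the plan says.** Four places bear on this point.

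- **Who may enter.** Section 3.1 says the study "will enroll either patients undergoing SCP or patients who have already had the SCP procedure". Eligibility criterion 2 in Section 4.1 repeats this: "Patient has agreed to undergo the SCP procedure or has already undergone the procedure". The synopsis carries the same criterion, and Section 4.2 extends the invitation to both groups.
- **When study work may start.** Section 4.2: "No study activities will be performed prior to patient signature of the informed consent form". Section 4.4 opens in the same sense: "This section is applicable to individuals who have undergone screening, have signed an Informed Consent Document".
- **What must be collected, and when.** Section 4.4.1: "Prior to surgery, the data in Table 1 must be collected for each enrolled Subject". No exception follows. Table 1 holds Form 1, which staff complete, and Form 2, whose questionnaires the subject completes. Some Form 1 items are worded for looking back, for example "Authorized medical personnel will collect basic demographics from the preoperative time period". Form 2 has no such wording.
- **What the data are for.** Section 4.5 plans to use patient features, including symptom severity, to identify suitable candidates and as covariates for post-operative outcomes. It does not say how an absent, recalled or late baseline would be handled.

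**The concern.** A stated rule fails for a stated part of the population. A site that enrols an already-operated patient has to fill or leave empty a form that should have been completed before the patient was in the study. It could use a charted score, the patient's recollection, the patient's present state, or a blank. Up to 30 sites are planned, and they may choose differently.

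The Form 2 pain and function scores are the evident measures of symptom severity, and severity is one of the features Section 4.5 names. If scores of different origin enter that analysis as though they were the same measurement, the estimated relation between severity and outcome may be too weak or too strong. That relation is what the study would use to say who is a suitable candidate.

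**Working it through.** **Step 1: the text.** Take a patient who consents after surgery.

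1. Sections 3.1 and 4.1 make this patient eligible.
2. Section 4.2 bars study collection before consent, hence before this patient's surgery.
3. Section 4.4.1 requires Form 2 before surgery from this patient as an enrolled subject.
4. Items 2 and 3 are compatible only if a self-completed score from routine care, dated before surgery, already exists. The protocol does not name this source.
5. Without such a score the baseline is missing, or it is recalled or taken after surgery, which is contrary to Section 4.4.1.

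The look-back wording eases the conflict for some Form 1 items but not for Form 2. The Form 1 eligibility check likewise cannot be done before surgery for this patient. Tables 1 to 3 list no item for baseline source.

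**Step 2: what can be identified.** Consent forms are dated (Section 4.3), and follow-up is timed from surgery, so the two dates separate the entry types. Within the already-operated group, the items the protocol lists do not separate charted, recalled and post-surgery scores.

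**Step 3: illustrative size.** The plan gives no figure to reproduce. Its only relevant number is the goal of about 1000 patients (Section 3.3), with no split by entry type. Every other input is assumed:

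- p: share of patients whose post-surgery score is entered as baseline (5%, 10%, 25%, 50%, that is 50, 100, 250 or 500 of 1000).
- SD 2 for baseline, post-surgery score and later outcome; mean fall of 4 after surgery.
- b: true slope of later outcome on pre-surgery severity, 0.1 to 0.5.
- ρ: correlation of the post-surgery score with the later outcome, 0.5 to 1.
- Both entry types share the same b and the same mean later outcome.

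Pooled slope = [(1−p)·b·4 + p·ρ·4] / [4 + 16·p(1−p)].

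Dividing by b gives the ratio to the true slope: [(1−p) + p·ρ/b] / [1 + 4p(1−p)].

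The ratio rises with ρ/b. Its lowest value is at ρ/b = 0.5/0.5 = 1 and its highest at ρ/b = 1/0.1 = 10.

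| p | Lowest: 1/[1+4p(1−p)] | Highest: (1+9p)/[1+4p(1−p)] |
|---|---|---|
| 5% | 1/1.19 = 0.84 | 1.45/1.19 = 1.22 |
| 10% | 1/1.36 = 0.74 | 1.90/1.36 = 1.40 |
| 25% | 1/1.75 = 0.57 | 3.25/1.75 = 1.86 |
| 50% | 1/2.00 = 0.50 | 5.50/2.00 = 2.75 |

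Adding only an entry-type term does not cure this. It removes the mean shift but not the mixed slopes, leaving (1−p) + p·ρ/b. That is 1.0 at ρ/b = 1 in every row; at ρ/b = 10 it is 1.45, 1.90, 3.25 and 5.50.

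**Step 4: recalled scores with random error only.** If the error is unrelated to outcome and the prospective baselines are error-free, the ratio is 1/[1 + p(1/rel − 1)]. With reliability 0.5 to 0.7 this gives 0.80–0.90 at p = 25% and 0.67–0.82 at p = 50%, so the slope is always weakened.

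**Step 5: using pre-surgery scores only.** With p = 0 the ratio is 1, given a common true slope. If no already-operated patient has a usable score, standard errors grow by 1/√(1−share): 1/√0.75 = 1.155 at a 25% share and 1/√0.50 = 1.414 at 50%.

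**The case against.** The strongest reply is that the text already excludes the worst outcome. Form 2 is a pre-operative form, due before surgery. A post-surgery score entered there breaks the protocol, and Section 8 has violations that affect data integrity logged. Read literally, an already-operated patient without a pre-surgery score simply has a missing baseline, which costs precision and representativeness but does not distort a slope.

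This stands in part. It is why the larger ratios are a worst case. It does not remove the conflict: the rule still cannot be met through study collection for an eligible group, and nothing tells a site to leave the form blank. Section 8 also says that lesser deviations are not collected, so logging depends on how a site classes a late form.

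Four stronger readings are tempting, and the documents do not support them.

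- *The analyst could not tell which rows are affected.* Consent and surgery dates identify the already-operated group. Only the source within it is open.
- *The database does not hold the source.* The case report forms are not supplied. What can be said is that the protocol does not specify that source be recorded.
- *Change-from-baseline results or re-operation risk are compromised.* Section 4.5 plans neither analysis.
- *Section 4.4.3 is a second contradiction, because early time points may precede consent.* Section 4.4 has follow-up forms sent to study subjects at the time points, so this needs only clearer wording.

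**Conclusion.** The conflict between the eligibility and consent rules and Section 4.4.1 is certain from the text, and so is the absence of a named baseline source. It should be fixed, because it touches the one analysis the protocol describes.

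The size of any bias is not known. The documents give neither the already-operated share nor the number with a score on file. The ratios hold only under the assumptions listed, and each supposes that every affected patient has a post-surgery score as baseline. At 5% or 10% affected the distortion is moderate. A reader might take 2.75 as the expected error, but it needs half the cohort affected, a true slope of 0.1 and perfect correlation between the score used as baseline and the later outcome, all at once. The direction is not fixed. If few already-operated patients enrol, or most have charted scores, the effect is small.

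**What to change.** 1. **Reconcile Sections 3.1, 4.1 and 4.2 with Section 4.4.1.** Limit the pre-surgery Table 1 requirement to subjects who consent before surgery. For already-operated subjects, accept Form 2 scores documented before the surgery date. Record baseline source (prospective, charted, recalled, post-surgery, none) and baseline date for everyone.
2. **Add to Section 4.5.** Base the main analyses that use Form 2 severity on scores dated before surgery. Use other baselines only in a labelled sensitivity analysis. Report results by entry type, derived from the consent and surgery dates.
3. **Clarify Section 4.4.3.** One sentence saying that Table 3 is required only at time points after consent.

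The cost is a few sentences and one data field with its date. The price in the analysis is precision: if no already-operated patient has a pre-surgery score, standard errors in the severity analyses rise by about 15% at a 25% share and 41% at 50%. Those results then describe only patients with a pre-surgery score, and the report should say so.
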